8.3. Visit 3 Procedures (Week 4 \pm 5 Days)

- Current medical condition review.

- Limited physical examination.
- Vital signs.
- Weight.
- Clinical laboratory tests.
- Urine pregnancy test.
- [REDACTED]
- IMP accountability.
- Study diary review.
- Contact IXRS and dispense IMP kits.
- AEs and concomitant medications.

8.4. Visit 4 Procedures (Week 8 ± 5 Days)

- Current medical condition review.
- Limited physical examination.
- Vital signs.
- Weight.
- Clinical laboratory tests.
- [REDACTED]
- Urine pregnancy test.
- Urinalysis.
- [REDACTED]
- [REDACTED]
- IMP accountability.
- Study diary review.
- Contact IXRS and dispense IMP kits.
- AEs and concomitant medications.

8.5. Visit 5 Procedures (Week 12 ± 5 Days)

- Current medical condition review.
- Limited physical examination.
- Vital signs.
- Weight.

- Clinical laboratory tests.
- Nonfasting lipid panel.
- HbA1c.
- Urine pregnancy test.
- [REDACTED]
- IMP accountability.
- Study diary review.
- Contact IXRS, dispense IMP kits.
- AEs and concomitant medications.

8.6. Visit 6 Procedures (Week 16 ± 5 Days)

- Current medical condition review.
- Limited physical examination.
- Vital signs.
- Weight.
- Clinical laboratory tests.
- [REDACTED]
- Urine pregnancy test.
- Urinalysis.
- [REDACTED]
- [REDACTED]
- IMP accountability.
- Study diary review.
- Contact IXRS and dispense IMP kits.
- AEs and concomitant medications.

8.7. Visit 7 Procedures (Week 20 ± 5 Days)

- Current medical condition review.
- Limited physical examination.
- Vital signs.
- Weight.
- Clinical laboratory tests.

- Urine pregnancy test.
- [REDACTED]
- IMP accountability.
- Study diary review.
- Contact IXRS and dispense IMP kits.
- Dispense 24-hour urine collection materials.
- AEs and concomitant medications.

8.8. Visit 8 Procedures (Week 24 ± 5 Days)

- Current medical condition review.
- Limited physical examination.
- Vital signs.
- Weight.
- Clinical laboratory tests.
- Nonfasting lipid panel.
- HbA1c.
- [REDACTED]
- Urine pregnancy test.
- Urinalysis.
- [REDACTED]
- [REDACTED]
- [REDACTED]
- IMP accountability.
- [REDACTED]
- [REDACTED]
- Study diary retraining.
- Study diary review.
- Contact IXRS and dispense IMP kits.
- AEs and concomitant medications.

8.9. Visit 9 Procedures (Week 26 + 5 Days)

- Current medical condition review.

- Limited physical examination.
- Vital signs.
- Weight.
- Urine pregnancy test.
- [REDACTED]
- IMP accountability.
- Study diary review.
- Contact IXRS and dispense IMP kits.
- AEs and concomitant medications.

8.10. Visit 10 Procedures (Week 30 ± 5 Days)

- Current medical condition review.
- Limited physical examination.
- Vital signs.
- Weight.
- Clinical laboratory tests.
- Urine pregnancy test.
- [REDACTED]
- IMP accountability.
- Study diary review.
- Contact IXRS and dispense IMP kits.
- AEs and concomitant medications.

8.11. Visit 11 Procedures (Week 34 ± 5 Days)

- Current medical condition review.
- Limited physical examination.
- Vital signs.
- Weight.
- Clinical laboratory tests.
- [REDACTED]
- Urine pregnancy test.
- Urinalysis.

- [REDACTED]
- [REDACTED]
- IMP accountability.
- Study diary review.
- Contact IXRS and dispense IMP kits.
- AEs and concomitant medications.

8.12. Visit 12 Procedures (Week 38 ± 5 Days)

- Current medical condition review.
- Limited physical examination.
- Vital signs.
- Weight.
- Clinical laboratory tests.
- Nonfasting lipid panel.
- HbA1c.
- Urine pregnancy test.
- [REDACTED]
- IMP accountability.
- Study diary review.
- Contact IXRS and dispense IMP kits.
- AEs and concomitant medications.

8.13. Visit 13 Procedures (Week 42 ± 5 Days)

- Current medical condition review.
- Limited physical examination.
- Vital signs.
- Weight.
- Clinical laboratory tests.
- [REDACTED].
- Urine pregnancy test.
- Urinalysis.
- [REDACTED]

- [REDACTED]
- IMP accountability.
- Study diary review.
- Contact IXRS and dispense IMP kits.
- AEs and concomitant medications.

8.14. Visit 14 Procedures (Week 46 ± 5 Days)

- Current medical condition review.
- Limited physical examination.
- Vital signs.
- Weight.
- Clinical laboratory tests.
- Urine pregnancy test.
- [REDACTED]
- IMP accountability.
- Study diary review.
- Contact IXRS and dispense IMP kits.
- Dispense 24-hour urine collection materials.
- AEs and concomitant medications.

8.15. Visit 15 Procedures (Week 50 ± 5 Days)

- Current medical condition review.
- Limited physical examination.
- Vital signs.
- Weight.
- Clinical laboratory tests.
- Nonfasting lipid panel.
- HbA1c.
- [REDACTED]
- Urine pregnancy test.
- Urinalysis.
- [REDACTED]

- [REDACTED]
- [REDACTED]
- [REDACTED]
- [REDACTED]
- Study diary review.
- IMP accountability.
- Contact IXRS.
- AEs and concomitant medications.

8.16. End of Study/Early Termination Visit Procedures

All subjects will have an End of Study/Early Termination Visit 4 weeks after their last dose of IMP.

Subjects receiving IMP 3x/week, will have IMP tapered to 2x/week for 2 weeks at Week 50 and then discontinued. These subjects will return at Week 56 + 5 days for their End of Study Visit.

Subjects receiving IMP 2x/week will discontinue dosing without a taper. These subjects will return at Week 54 + 5 days for their End of Study Visit.

Subjects who discontinue study participation at any other time in the study will have their dose tapered to 1 mL SC 2x/week (if required) and return for the Early Termination Visit 4 weeks after their last dose of IMP.

The following assessment will be done at the End of Study/Early Termination Visit

- Current medical condition review.
- Complete physical examination.
- Vital signs, including weight.
- Clinical laboratory tests.
- Urine pregnancy test.
- Urinalysis
- IMP accountability (subjects who required taper only).
- Study diary review.
- Contact IXRS.
- AEs and concomitant medications.

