1.4. Schedule of Study Events

Table 1: Schedule of Study Events

Period	Screening (Day -63 to -3)	Baseline	Open Label/Open-label Extension													Taper Safety Visit ^a	End of Study/Early Termination ^b
			3	4	5	6	7	8	9	10	11	12	13	14	15		
VISIT #: Visit window is ± 5 days starting with Visit 2 (except at V9 where window is + 5 days only)	1	2															
Week		0	4	8	12	16	20	24	26	30	34	38	42	46	50		54 or 56
Informed consent ^c	X																
Inclusion/exclusion criteria review	X	X															
Demographics	X																
Medical/surgical history	X																
Current medical condition review	X	X	X	X	X	X	X	X	X	X	X	X	X	X	X	X	X
Complete physical examination	X																
Limited physical examination		X	X	X	X	X	X	X	X	X	X	X	X	X	X	X	
Vital signs	X	X	X	X	X	X	X	X	X	X	X	X	X	X	X	X	X
Height (screening only) and weight	X	X	X	X	X	X	X	X	X	X	X	X	X	X	X	X	X
Clinical laboratory tests (serum chemistry and CBC w/diff)	X	X	X	X	X	X	X	X		X	X	X	X	X	X	X ^d	X
HbA1c	X				X			X				X			X		
Nonfasting lipid panel		X			X			X				X			X		
██████████		X		X		X		X			X		X		X		
██████	X	X		X		X		X			X		X		X		

Period	Screening (Day -63 to -3)	Baseline	Open Label/Open-label Extension													Taper Safety Visit ^a	End of Study/Early Termination ^b
			3	4	5	6	7	8	9	10	11	12	13	14	15		
VISIT #: Visit window is ± 5 days starting with Visit 2 (except at V9 where window is + 5 days only)	1	2	3	4	5	6	7	8	9	10	11	12	13	14	15		
Week		0	4	8	12	16	20	24	26	30	34	38	42	46	50		54 or 56
██████████	X																
████████████████████		X		X		X		X			X		X		X		
Serum pregnancy test	X																
IGRA for TB	X																
██████████	X	X		X		X		X			X		X		X		X
Urine pregnancy test		X	X	X	X	X	X	X	X	X	X	X	X	X	X	X	X
██████████	X	X	X	X	X	X	X	X	X	X	X	X	X	X	X		
████████████████████ ^s	X						X							X			
██████████		X						X							X		
██████████	X																
IXRS contact	X	X	X	X	X	X	X	X	X	X	X	X	X	X	X	X	X
IMP and diary training		X						X							X ^f		
IMP accountability			X	X	X	X	X	X	X	X	X	X	X	X	X	X	X ^f
Dispense IMP kits		X	X	X	X	X	X	X	X	X	X	X	X	X	X ^f		
Administer first dose ^g		X															
Diary review			X	X	X	X	X	X	X	X	X	X	X	X	X	X	X
██████████		X						X							X		

Period	Screening (Day -63 to -3)	Baseline	Open Label/Open-label Extension													Taper Safety Visit ^a	End of Study/Early Termination ^b	
			3	4	5	6	7	8	9	10	11	12	13	14	15			
VISIT #: Visit window is ± 5 days starting with Visit 2 (except at V9 where window is + 5 days only)	1	2																

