4. OBJECTIVES

4.1. Primary Objective

Primary Objective	Primary Endpoints
To confirm the safety and tolerability of Acthar in the induction of remission of proteinuria in subjects with primary FSGS who are resistant to, or intolerant of, at least 1 prior immunosuppressive therapy	
 ● Severity and frequency of adverse events (AEs) ● Changes in physical findings ● Changes in clinical laboratory findings ● Changes in vital signs

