10.6. Height and Weight

Height will be collected at screening only. Weight will be collected at specified times during the study.

10.7. Clinical Laboratory Tests, HbA1c, Serum Cystatin C, Serum Electrolytes, IGRA, Urinalysis, and Pregnancy Tests

The clinical laboratory tests are listed in [Section 24.1](#). All clinical laboratory tests will be done at a central laboratory facility except urine pregnancy (at the site) and IGRA (local laboratory). Specific instructions for collection, storage and shipment of clinical laboratory samples will be provided in a separate laboratory manual.

Samples for laboratory testing at all visits may be collected under fasted or nonfasted conditions. The date and time of the sample collection must be documented on the laboratory report. Investigators must review and sign laboratory reports. The clinical significance of each laboratory abnormality will be documented. New clinically significant laboratory abnormalities or clinically significant changes in laboratory values will be reported as AEs, as appropriate.

Hematology with differential, serum chemistry, other specific tests, and urinalysis samples will be collected at the specific times starting at screening and throughout the study.

In addition:

- All female subjects of child-bearing potential will have a serum pregnancy test at the Screening Visit/Visit 1, and a urine pregnancy test at the Baseline Visit/Visit 2 and at specified visits throughout the study. Results must be available prior to dosing with protocol mandated IMP. Subjects with positive results will be ineligible for study entry (Screening Visit/Visit 1) or withdrawn from the study. Any female subject that becomes pregnant during the study will be immediately withdrawn and the pregnancy report as per [Section 13.5](#).

If applicable, the subject's agreement to use contraception throughout their study participation, and for 4 weeks after ending study participation, will be documented.

- HBsAg and HBcAb will be performed at the Screening Visit/Visit 1. Results of these tests must be negative or nonreactive for subjects to qualify for the study.
- HCV will be performed at the Screening Visit/Visit 1. A positive HCV will automatically trigger a HCV PCR analysis. HCV PCR must be < 25 IU/mL to qualify for the study.

[REDACTED]

[REDACTED]

[REDACTED]

[REDACTED]

[REDACTED]

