12.7.2. Clinical Laboratory Tests

Clinical laboratory testing will be presented in data listings.

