24. ATTACHMENTS

24.1. Attachment 1: Clinical Laboratory Tests

Serum Chemistry	
Alanine aminotransferase (ALT)	Creatinine
Albumin (total)	Cystatin C
Alkaline phosphatase	Glucose
Aspartate aminotransferase (AST)	Hemoglobin A1c
Bilirubin (total)	Phosphorus
Blood urea nitrogen	Potassium
Calcium	Protein, total
CO ₂	Sodium
Chloride	Uric acid
Lipid Panel	
Total cholesterol	LDL
HDL	Triglycerides
Hormones	
Serum and urine beta-human chorionic gonadotropin (pregnancy test)	
Hematology Assays	
Hematocrit	Platelet count
Hemoglobin	Red blood cell count
White blood cell count, including differential	Absolute neutrophil count
Urinalysis	
Blood	Nitrite
Clarity	Nitrite
Color	Protein
Glucose	pH
Leukocyte esterase	Specific gravity
Ketones	

Serum Chemistry	
Hepatitis Serology	
Hepatitis B core antibody	Hepatitis C virus antibody (HCV)
Hepatitis B surface antigen	Hepatitis C virus PCR (only if HCV +)
TB Assay	
Interferon gamma release assay (IGRA) (obtained at local lab)	

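### HbA1c and the nonfasting lipid panel are not scheduled at Early Termination in Table 1 or Section 8.16, Attachment 1 conflicts with them on HbA1c, and early leavers may lack a recent or any post-baseline value

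*Combined protocol and SAP*

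**What the plan says.** One of the four primary endpoints in Section 4.1 is "Changes in clinical laboratory findings". Three places govern whether HbA1c and lipids are measured when a subject leaves early.

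- **Table 1 (Section 1.4).** HbA1c is marked at Screening and Weeks 12, 24, 38 and 50. The row "Nonfasting lipid panel" is marked at Baseline and the same four weeks. Both rows are blank under the Taper Safety Visit and under End of Study/Early Termination. The row beginning "Clinical laboratory tests (serum chemistry and CBC w/diff" is marked at End of Study/Early Termination.
- **Section 8.16.** Under "The following assessment will be done at the End of Study/Early Termination Visit" the list includes clinical laboratory tests and urinalysis. HbA1c and lipids do not appear. The lists for Weeks 12, 24, 38 and 50 (Sections 8.5, 8.8, 8.12 and 8.15) name both as items separate from clinical laboratory tests.
- **Section 10.7 and Attachment 1 (Section 24.1).** Section 10.7 says "The clinical laboratory tests are listed in" Section 24.1. That attachment puts "Hemoglobin A1c" in the serum chemistry block, next to glucose. Lipids have their own block.

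On analysis, Section 12.7.2 says "Clinical laboratory testing will be presented in data listings". No laboratory summary by visit, last-value summary or rule for missing laboratory values is given there.

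**The concern.** Section 3.5 names hyperglycemia as a known risk of the drug. HbA1c above 8% is one of the diabetic criteria for both dose reduction (9.3.1) and treatment discontinuation (9.3.2). Section 14.1 sends leavers to the Section 8.16 assessments and does not replace dosed subjects who withdraw. For an early leaver, that visit is therefore the last scheduled chance to obtain these values.

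Two things are at stake. First, a change from baseline cannot be shown for a subject with no post-baseline value, and change is what the endpoint names. Second, sites can read the HbA1c requirement in two ways, so collection at Early Termination may differ between sites for reasons unrelated to the subjects.

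**Working it through.** The plan states no figure on this point: there is no sample size calculation (12.9), no dropout rate and no missing-data rule. The check is therefore a reading of the schedule plus simple arithmetic in nominal study weeks.

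**1. Which reading of HbA1c fits the schedule.** Table 1 marks chemistry at 14 of the 15 numbered visits (all but Visit 9), at End of Study/Early Termination, and conditionally at the Taper Safety Visit. It marks HbA1c at 5 numbered visits. If Attachment 1 is taken literally, HbA1c is also due at the other 14 − 5 = 9 numbered visits and at Early Termination, and its own row in Table 1 is redundant. The separate row and the separate items in Section 8 suggest that HbA1c is not due at Early Termination. Section 10.7 with Attachment 1 says that it is. No section settles this. Lipids have no alternative reading: they are not due.

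**2. Age of the last scheduled value at stopping** (Table 1 reading).

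| Subject stops in weeks | Last HbA1c | Last lipids | Longest lag to stopping |
|---|---|---|---|
| 0 to 12 | Screening only | Baseline only | no post-baseline value |
| 12 to 24 | Week 12 | Week 12 | 24 − 12 = 12 weeks |
| 24 to 38 | Week 24 | Week 24 | 38 − 24 = 14 weeks |
| 38 to 50 | Week 38 | Week 38 | 50 − 38 = 12 weeks |

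The Early Termination visit is 4 weeks after the last dose, or 6 weeks after the decision to stop if a 2-week taper comes first. By that visit the last value can be 14 + 4 = 18 to 14 + 6 = 20 weeks old. By contrast, the longest gap between scheduled chemistry draws during treatment, and so between glucose values, is 6 weeks (Week 24 to Week 30).

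**3. Share of leavers with no post-baseline value.** If departures are uniform over 50 weeks, the share before Week 12 is 12/50 = 24%.

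**4. Number of subjects.** Take N = 60 and an assumed total dropout d. Uniform departures give 60 × d × 0.24. A constant hazard gives 60 × [1 − (1 − d)^(12/50)].

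| Assumed dropout d | Leavers | Before Week 12, uniform | Before Week 12, constant hazard | Share of leavers, constant hazard |
|---|---|---|---|---|
| 10% | 6 | 1.4 | 1.5 | 25% |
| 20% | 12 | 2.9 | 3.1 | 26% |
| 30% | 18 | 4.3 | 4.9 | 27% |
| 40% | 24 | 5.8 | 6.9 | 29% |
| 50% | 30 | 7.2 | 9.2 | 31% |

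The dropout range is an assumption.

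**The case against.** The strongest reply is that little is lost, and most of its parts stand.

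- A reader might infer that leavers, including those who stop for hyperglycemia, have no final value. The documents do not support this. Leavers after Week 12 have an earlier on-treatment value. A subject stopped on the diabetic criteria generally has the HbA1c or glucose result that triggered the stop. Glucose is drawn at Early Termination.
- A reader might infer that the laboratory endpoint as a whole is informatively missing. It is not. Chemistry, blood count and urinalysis are all collected at that visit, and the gap is two tests. For HbA1c, dependence on outcome is plausible because it is a stopping criterion. For lipids no such link exists in the documents, since no taper or stopping rule uses them.
- A reader might infer that planned summaries would understate the change. Section 12.7.2 plans listings only, so no planned estimate is there to be biased.
- Clinically significant laboratory changes are also reported as adverse events (10.7), and events leading to discontinuation are summarised (12.7.1). Unscheduled tests are allowed (Section 10).
- A test at Early Termination is an off-drug value and does not replace a missing on-treatment one.

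Three things remain. Glucose does not fully stand in for HbA1c, because Section 10.7 allows fasted or nonfasted samples, whereas the diabetic criteria need either a fasting value or a random value with symptoms. Unscheduled tests are permitted, not required. And a listing cannot show a change for someone with no post-baseline result.

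**Conclusion.** The point holds in a limited form. Table 1 and Section 8.16 omit HbA1c and lipids at Early Termination. Section 10.7 with Attachment 1 contradicts them on HbA1c, and nothing contradicts them on lipids. Leavers before Week 12 may have no post-baseline value of either test: 24% of leavers under uniform departure, 25% to 31% under a constant hazard. In numbers, that is roughly 1.5 to 9 of 60 subjects across an assumed 10% to 50% dropout. Later leavers may have a value up to 14 weeks old at stopping.

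These figures rest on nominal visit weeks, on assumed departure patterns, and for HbA1c on the Table 1 reading. Informative missingness of HbA1c is a reasonable suspicion that the documents do not establish. This is a modest, inexpensive improvement to the data for a primary endpoint, not a flaw that undermines the study.

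**What to change.** 1. Reconcile Table 1, Section 8.16 and Attachment 1 so that all three say the same about HbA1c at Early Termination.
2. Add HbA1c and the nonfasting lipid panel at the Early Termination visit, through a footnote limited to subjects without a Week 50 value. The footnote is needed because Table 1 and Section 8.16 treat End of Study and Early Termination as one visit, and completers already have Week 50 results.
3. Label these results as post-treatment, taken 4 weeks after the last dose. Show them separately from on-treatment values in the laboratory listings and in any change-from-baseline presentation.

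The cost is two assays per early terminator at a visit where blood is already taken. Whether the existing sample suffices should be checked against the laboratory manual, which is a separate document. No visit is added and no dosing or stopping rule changes. The limitation is that an off-drug value is not interchangeable with a Week 50 value, so it adds information on early leavers without filling the on-treatment gap.

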8.17. Taper Safety Visit

- Current medical condition review.
- Limited physical examination.

- Vital signs.
- Weight.
- Clinical laboratory tests (if the reason for discontinuation was related to laboratory test results).
- IMP accountability.
- Study diary review.
- AEs and concomitant medications.

9. INVESTIGATIONAL MEDICINAL PRODUCT

9.1. Methods of Assigning Subjects to Treatment Groups

The investigator or designee will contact IXRS to register subjects at Visit 1. The subject's identification (ID) number will be determined by the IXRS and will be used to identify the subjects for the duration of the study within all systems and documentation. Subject ID numbers will consist of 7 digits: the first 4 digits reflect the site number assigned to the Investigator and the last 3 digits are the subject number.

A subject ID number will not be assigned to more than 1 subject. If a subject is not eligible to receive treatment, or should a subject discontinue from the study, the subject ID number cannot be reassigned to another subject.

In the event that a subject is rescreened within the screening window, they do not need a new subject ID number. At the Baseline Visit/ Visit 2, qualified subjects who meet all of the eligibility criteria will be enrolled into the study. The investigator or designee must contact IXRS to record each subject visit and receive the IMP kit assignments.

The investigator or designee must contact the IXRS to report subjects as a screen failure if the enrolled subject does not meet eligibility criteria at the Baseline Visit/Visit 2.

The investigator or designee must contact the IXRS to report all subject visits and status changes.

The investigator must maintain a subject master log linking the subject ID to the subject's name. The investigator must follow all applicable privacy laws in order to protect a subject's privacy and confidentiality. Information that could identify a subject will be masked on material received by the sponsor.

9.2. Emergency Identification of Investigational Medicinal Product

This is an unblinded study.

9.3. Dosing Procedures

The following Acthar treatments are to be administered. The study treatment schedule is as noted in [Table 5](#).

Table 5: IMP Treatment Schedule

Study Week	Study Period	Study Drug	Dose
Weeks 0 to 50	Open Label/Open-label Extension	Acthar	1 mL SC 3x/week ^a
Weeks 50 to 51 ^b	Follow-up Period (taper)	Acthar	1 mL SC 2x/week

^aDose can be tapered to 1 mL SC 2x/week for safety and/or tolerability reasons. If a subject ends study participation prior to Week 50, the dose of Acthar should be tapered to 1 mL SC 2x/week for 2 weeks.

^bSubjects receiving Acthar 1 mL (80 U) SC 3x/week should be tapered to 1 mL SC 2x/week for 2 weeks, with a final visit 4 weeks after the last dose of Acthar. Subjects in the open-label extension receiving 1 mL SC 2x/week at Week 49 will stop dosing at the conclusion of Week 49, with a final Visit 4 weeks after the last dose of Acthar.

The subject or subject's caregiver will administer the first dose of IMP in the clinic under the supervision of study staff. The subject will remain in the clinic for at least 1 hour post dose to monitor for allergic or anaphylactic reaction(s). After Visit 2, all doses will be administered by the subject or the subject's caregiver at home.

Throughout the trial, IMP cannot be taken on 2 consecutive days and cannot be taken more than 3 days apart, regardless of dosing frequency.

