Protocol Number: MNK14224049	Type: Phase 4 (US)/Phase 2 (all other countries)
Condition/Disease: Idiopathic focal segmental glomerulosclerosis (FSGS)	
Investigational Medicinal Product and Treatment Administration: Acthar 1 mL (80 U) SC 3x/week will be administered to all subjects from Week 0 to 50. Tapering of dose to 1 mL SC 2x/week will be allowed for safety and/ tolerability issues. Once the dose is tapered to 1 mL SC 2x/week it must remain at this level. Subjects unable to tolerate 1 mL SC 2x/week will be discontinued.	
Efficacy Evaluations: There are no efficacy assessments.	
Safety Evaluations: The following safety assessments will be evaluated: adverse events, physical examinations, clinical laboratory tests, vital signs, medical and surgical history, height and height.	
Exploratory Evaluations: The following exploratory assessments will be evaluated: [REDACTED] [REDACTED] [REDACTED]	
Statistical Methods: Analysis Populations: Intent-to-Treat (ITT) Population: All enrolled subjects who receive 1 or more doses of IMP and who contribute any exploratory data to the study. Per-Protocol Population: the subset of the ITT population who complete the study as per protocol. Completer populations will be further defined in the statistical analysis plan. Safety Population: all enrolled subjects who receive 1 or more doses of IMP. Sample Size: Approximately 60 subjects will be enrolled. Formal sample size calculations were not performed. Assessments: Efficacy: There are no efficacy endpoints. Safety: The following safety assessments will be evaluated: adverse events, physical examinations, clinical laboratory tests, vital signs, medical and surgical history, height and height. Exploratory: Exploratory endpoints will be summaries with descriptive statistics only. [REDACTED] [REDACTED] [REDACTED] [REDACTED]	

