3.3. Dosage and Administration

Investigational medicinal product (IMP) will be used to denote active drug (Acthar) and/or matching placebo.

In this study all subjects will receive open label treatment with Acthar 1 mL (80 U) SC 3 times per week (3x/week) for 50 weeks. Taper to 1 mL SC twice a week (2x/week) for safety and/or tolerability reasons will be allowed. If the dose is tapered to 1 mL SC 2x/week it must remain at this level for the remainder of the study. Subjects unable to tolerate 1 mL SC 2x/week will be discontinued.

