9.3.1. Dose Reduction

The dosing of Acthar should be tapered from 3x/week to 2x/week for safety reasons if a subject meets any of the following criteria:

- Development of accelerated hypertension (defined as systolic blood pressure \geq 180 *and* diastolic blood pressure \geq 100 mm Hg) that cannot be managed with adjustment of concomitant medications such as antihypertensive medications.
- Development of an edema score of 4 at any visit that cannot be managed with adjustment of concomitant medications such as diuretics (see [Section 24.2](#)).
- Development of congestive heart failure that cannot be managed with adjustment of concomitant medications such as diuretics and antihypertensive medications.
- Development of diabetic signs/symptoms (ie, HbA1c > 8%, or fasting plasma glucose > 126 mg/dL, or classic symptoms of hyperglycemia with random plasma glucose > 200 mg/dL).
- Development of any other AE of at least moderate intensity that cannot be managed with adjustment of concomitant medications.

Any subject whose dose is tapered for any of the reasons described above will have a Taper Safety Visit scheduled 2 weeks after the start of the taper.

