9.7. Compliance Monitoring

Prior to beginning the administration of IMP, subjects and/or their caregiver will be trained on dosing administration and must exhibit proper technique. Subjects and/or their caregiver will be trained on the completion of the study diary and will complete a study diary entries to record all IMP administration and will bring it, along with all IMP kits including used vials to each visit. Each time IMP is dispensed compliance will be encouraged. Subject diary training is an ongoing process as the diary will be reviewed with the subject at each visit to monitor compliance with IMP administration.

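### Counted in calendar days, Section 9.3's 3-day maximum interval can be kept for at most 3 weeks after a reduction to 2x/week, yet that reduction is permanent

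*Combined protocol and SAP*

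**What the plan says.** Section 9.3 sets both a minimum and a maximum spacing, and applies them to every frequency: "Throughout the trial, IMP cannot be taken on 2 consecutive days and cannot be taken more than 3 days apart, regardless of dosing frequency".

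All subjects start on 80 U three times a week. Reduction to twice a week cannot be reversed. The synopsis says "Once the dose is tapered to 1 mL SC 2x/week it must remain at this level", and Section 3.3 says "If the dose is tapered to 1 mL SC 2x/week it must remain at this level for the remainder of the study"; Section 5.1 repeats this. The only other course is discontinuation, for subjects who cannot tolerate 2x/week.

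Section 9.3.1 makes the reduction a safety measure: "The dosing of Acthar should be tapered from 3x/week to 2x/week for safety reasons if a subject meets any of the following criteria". The criteria are unmanaged accelerated hypertension, an edema score of 4, congestive heart failure, diabetic signs or symptoms, and other adverse events of at least moderate intensity. Such a subject "will have a Taper Safety Visit scheduled 2 weeks after the start of the taper".

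Dosing is largely unsupervised: "After Visit 2, all doses will be administered by the subject" or a caregiver at home. Section 9.7 provides that "the diary will be reviewed with the subject at each visit to monitor compliance with IMP administration", and Section 8.17 lists "Study diary review" and IMP accountability at the Taper Safety Visit.

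No section exempts 2x/week from the 3-day limit, and none defines how days apart are counted.

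**The concern.** Two instructions bind the same subject, and after a few weeks they cannot both be followed. The subjects affected are those reduced for safety or tolerability, who inject at home and whose diaries are checked for compliance.

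The plan does not say which instruction prevails. If the weekly frequency prevails, a subject who follows the reduced dose faithfully departs from Section 9.3 week after week, and Section 18.1 requires investigators to notify the IRB/IEC of deviations according to local requirements. If the interval prevails, the subject receives more drug than the reduced level intends. That dose has a further use: Section 9.3.2 bases some discontinuations on whether the reduction to 2x/week, together with adjustment of other medication, has controlled the event.

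**Working it through.** The plan offers no calculation on this point to reproduce.

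**Inputs**
- Gap between doses: at least 2 and at most 3 calendar days (Section 9.3).
- Full schedule: 3 doses of 80 U per week, 240 U/week (Section 5.1).
- Reduced schedule: 2 doses of 80 U per week, 160 U/week, kept for the rest of the study (synopsis, Sections 3.3 and 5.1).
- Assumptions: a gap is the difference between calendar dates (Monday to Thursday is 3 days), and reduced weeks are consecutive 7-day blocks with exactly two doses each.

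**1. Average gap.** 7 / 2 = 3.5 days, or 84 hours, against a limit of 3 days, or 72 hours.

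**2. Fixed weekly patterns.** There are 21 pairs of days in a week. Removing the 7 consecutive pairs leaves 14. Seven have gaps of 3 and 4 days; seven have gaps of 2 and 5 days. All 14 exceed 3 days.

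**3. Drifting patterns.** Two gaps of at most 3 days cover at most 6 of 7 days, so the first dose of each week must fall at least one day earlier than in the week before. The last 3x/week dose falls no later than the day before the first reduced week, so the first reduced dose falls no later than day 3. The best case is days 3, 6 | 9, 12 | 15, 18. The next dose is due by day 21, which would be a third dose in week 3; waiting until day 22 makes a gap of 4 days.

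| Last 3x/week dose before the reduction starts | First reduced dose by | Weeks both rules hold |
|---|---|---|
| 1 day before | day 3 | 3 |
| 2 days before | day 2 | 2 |
| 3 days before | day 1 | 1 |

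An exhaustive enumeration of dosing days gives the same 3, 2 and 1. Allowing 3.5 days instead of 3 still gives 3 weeks. Ignoring the gap from the last 3x/week dose gives 4 weeks, but that start itself breaks the rule.

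**4. What would work.** With a 4-day maximum, 2x/week is feasible without limit (3 + 4 = 7; the enumeration ran to 60 weeks). At 3x/week the present 3-day limit is always feasible (2 + 2 + 3 = 7).

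**5. Dose under each way out**

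| Conduct | Doses/week | U/week | Reduction from 3x/week |
|---|---|---|---|
| Keep 2x/week (e.g. Monday/Thursday) | 2 | 160 | 1 − 2/3 = 33.3% |
| Keep the interval (every 3 days) | 7/3 = 2.33 | 186.7 | 1 − (7/3)/3 = 22.2% |

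The first breaks the interval rule once a week. The second adds 0 or 1 dose by day 14, 1 or 2 by day 28, and 2 by day 42, relative to 2x/week.

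**6. The 2-week taper at Week 50.** For a Monday/Wednesday/Friday subject, the weeks that can be kept by taper start day are: Monday 1, Tuesday 3, Wednesday 2, Thursday 3, Friday 2, Saturday 3, Sunday 2. Six of the seven start days allow a compliant 2-week taper. Example: last full-schedule dose on Wednesday, taper from Thursday, doses on Saturday, Tuesday, Friday and Monday.

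**The case against.** The best defence is that the key term is undefined. If days apart means dose-free days, Monday/Thursday has 2 and 3 dose-free days and complies indefinitely. The Amendment 2.1 summary records the sentence as a deliberate dosing restriction, and its reference to any dosing frequency suggests that its drafters thought it workable at more than one. This stands as a doubt about intent. It does not rescue the text: in ordinary usage Monday and Thursday are three days apart, a reading in hours (72 against 84) also fails, and the dose-free reading would itself have to be written down.

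The second defence is that little follows in practice. The 2x/week level is stated repeatedly and as mandatory, so sites will most likely keep it and let the interval run a day over. Diary review and accountability at the Taper Safety Visit and later visits could catch anyone who puts the interval first. This stands, and it limits the weight of the point. A reader might infer that subjects reduced for safety will be overdosed. The documents do not support that: the 2.33 doses/week is a hypothetical consequence of one choice, and at most one extra dose would have accrued by the 2-week visit.

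Third, the 3-day cap may be intended to match the 24 to 72 hours between doses in the prescribing information cited in Section 3.4. The documents do not say so, and no sustained 2x/week schedule can meet 72 hours.

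**Conclusion.** The point holds: a subject permanently reduced to 2x/week cannot follow Section 9.3 for more than 1 to 3 weeks, depending on where the reduction starts relative to the last 3x/week dose. The likely size is about one interval breach per week for each such subject for the rest of treatment, with the intended 33% reduction intact. The number of such subjects is not known. The arithmetic is certain given calendar-day counting; the sponsor's intended meaning is less so.

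Three stronger inferences should not be drawn.
- A reader might extend the conflict to the routine taper at Week 50. That taper lasts only 2 weeks, Visit 15 has a window of 5 days either side, and no start weekday is prescribed, so it can usually comply.
- A reader might infer that the safety results are compromised. Section 12.7 includes every subject who receives at least one dose, whatever the spacing.
- A reader might infer that reduced subjects leave the Per Protocol Population. Section 12.2 does not say that an interval breach disqualifies a subject.

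This is a contradiction in a dosing instruction that should be corrected. It is not a threat to the study's conclusions.

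**What to change.** In Section 9.3, replace the single limit with one for each frequency. For example: doses are never taken on consecutive days; the maximum gap is 3 days at 3x/week and 4 days at 2x/week (for example Monday and Thursday); gaps are differences between calendar dates. Align the diary training and compliance checks with this.

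The downside is that 4 days is 96 hours, beyond the 72-hour labelled interval cited in Section 3.4. But a sustained 2x/week schedule averages 84 hours and already exceeds it, as did the twice-weekly regimen in the prospective study cited in Section 3.1 (3 FSGS patients). If the sponsor prefers to keep the 3-day cap, Section 9.3 should say which rule prevails at 2x/week.

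The cost is one sentence, carried by a protocol amendment as Section 16 requires, a sponsor decision on the 4-day limit, and matching site wording. Visits, sample size and analyses do not change.
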